#### Hypothetical data scenarios

Hypothetical data scenarios are shown in [Table 10.3: 1](#). These scenarios reflect potential on-study data constellations and related escalation as allowed by the model and the planned dose groups. It is assumed that each cohort has exactly three patients who are all evaluable. For each scenario, the probability of overdose for the current dose, as well as the next potential dose and related probabilities of target dosing and over-dosing are shown.

For example, scenario 1 represents the case that no DLE is observed in 3 patients at the starting dose of 0.06 mg. In this case, the next planned dose permitted by the model and the 200% escalation rule is 0.18 mg. In contrast, scenario 2 assumes that there is one DLE observed in the first dose group. This would mean overtotoxicity from the beginning, and the recommendation would be to stop the trial.

In scenario 3, there is no DLE after the first 2 dose groups, which would allow the trial to continue to the next dose level. In scenario 4, the first DLE occurs in dose group 0.18 mg. Then the recommendation would be to repeat that dose. Scenario 5 shows that the trial would continue to the next dose level 0.5 mg if no additional DLE was observed in the 0.18 mg dose group.

However, if there was another DLE (as in scenario 6), then the recommendation would be to go back to dose 0.06 mg. If there was no further DLE then (scenario 7), one could go up again to dose 0.18 mg. Escalation to the next dose group would only be allowed in case there was no further DLE in this dose group in additional 6 patients (see scenarios 8 and 9).

Scenario 10 shows the case where the trial runs through up to the highest possible dose group 2 mg without any DLE and having observed a total of 18 patients (6 were required for the MTD). Scenarios 11 and 12 show that it is even possible to have one DLE in the 2 mg dose group and still to complete the trial with a total of 18 patients. However, if there were 2 DLEs in the highest dose group, then the model would recommend to return to dose 1 mg (scenario 13).

Table 10.3: 1 Hypothetical data scenarios

Scenario	Dose (mg)	# Pat.	# DLE	Current Dose: P(OD)	Next recomm. dose	Next dose:	
						P(TD)	P(OD)
1	0.06	3	0	0.016	0.18	0.968	0.032
2	0.06	3	1	0.308	N/A	N/A	N/A
3	0.06	3	0				
	0.18	3	0	0.011	0.5	0.964	0.036
4	0.06	3	0				
	0.18	3	1	0.182	0.18	0.818	0.182
5	0.06	3	0				
	0.18	6	1	0.074	0.5	0.789	0.211
6	0.06	3	0				
	0.18	6	2	0.290	0.06	0.874	0.126
7	0.06	6	0	0.062	0.18	0.808	0.192
	0.18	6	2				
8	0.06	6	0				
	0.18	9	2	0.105	0.18	0.895	0.105
9	0.06	6	0				
	0.18	12	2	0.049	0.5	0.773	0.227
10	0.06	3	0				
	0.18	3	0				
	0.5	3	0				
	1	3	0				
	2	6	0	0.010	2	0.990	0.010
11	0.06	3	0				
	0.18	3	0				
	0.5	3	0				
	1	3	0				
	2	3	1	0.220	2	0.780	0.220
12	0.06	3	0				
	0.18	3	0				
	0.5	3	0				
	1	3	0				
	2	6	1	0.098	2	0.902	0.098
13	0.06	3	0				
	0.18	3	0				
	0.5	3	0				
	1	3	0				
	2	6	2	0.327	1	0.961	0.039

## Operating characteristics

Operating characteristics are a way to assess the long-run behaviour of a model by illustrating the precision of the design in estimating the MTD. Under an assumed true dose-toxicity curve, metrics such as the probability of recommending a dose with true DLE rate in the target interval can be approximated via simulation. Table 10.3: 2 describes 6 assumed true dose-toxicity scenarios which were used to assess the operating characteristics of the model. These scenarios reflect a wide range of possible cases as follows:

- Scenario 1: aligned with prior medians
- Scenario 2: aligned with prior means
- Scenario 3: high-toxicity scenario
- Scenario 4: low-toxicity scenario
- Scenario 5: non-logistic dose-toxicity scenario
- Scenario 6: low-toxicity followed by high-toxicity

Table 10.3: 2 Assumed true dose-toxicity scenarios

Scenario	P(DLE)	Dose (mg)				
		0.06	0.18	0.5	1	2
1: Prior Med		0.007	0.014	0.030	0.053	0.101
2: Prior Mean		0.067	0.088	0.119	0.154	0.212
3: High Tox		0.100	0.150	0.200	0.280	0.400
4: Low Tox		0.001	0.005	0.012	0.086	0.127
5: Non-Logistic		0.040	0.010	0.180	0.280	0.360
6: Low-High		0.001	0.011	0.047	0.181	0.500

For each of these scenarios, 1000 trials were simulated. Each cohort consisted of 3 patients and dose escalation complied with the following rule:

*Escalate to the maximum dose which satisfies the overdose criterion and is  $\leq 200\%$  increase from the current dose.*

The MTD was considered reached if at least 6 patients have been evaluated at a dose level which is the model's recommendation for the next dose cohort. A minimum number of 15 patients in the trial was required, and the maximum allowed patient number was 21.

It was then assessed how often a dose was declared as MTD with true DLE rate in the targeted or in the overdosing range. Furthermore, the average, minimum and maximum number of patients per trial and the average number of DLEs per trial are reported. Results are shown in [Table 10.3: 3](#).

Table 10.3: 3

Simulated operating characteristics

Scenario	% of trials declaring a MTD with true DLT rate in		% of early stopped trials	# Patients	# DLEs
	[0, 0.25] target dosing	[0.25,1] overdosing		Mean (Min-Max)	Mean (Min-Max)
1	94.4	0	5.6	17.97 (3-21)	0.87 (0-4)
2	70.2	0	29.8	15.33 (3-21)	1.80 (0-6)
3	38.8	17.1	44.1	13.55 (3-21)	2.38 (0-6)
4	98.3	0	1.7	17.75 (3-21)	0.99 (0-4)
5	37.8	36.8	16.4	16.42 (3-21)	2.36 (0-6)
6	77.8	7	15.2	18.67 (3-21)	2.41 (0-6)

In scenario 1, which reflects the case that the true dose-toxicity is aligned with prior medians, 94.4% of the simulated trials declared a dose as MTD with true DLT rate in the targeted toxicity range. Note that 5.6% of the simulated trials stopped either because there was no MTD determined after 21 patients had been observed (3.5%) or because of high toxicity (2.1%). This latter is mostly due to the cases that 1 DLT is observed out of 3 patients at the starting dose of 0.06 mg. In reality, this situation would rarely happen as the safety profile of starting dose is expected to be good.

In scenario 2, the assumed dose toxicities are higher than in scenario 1. This results in a higher percentage of early stopped trials (about 30%). In this case, about 70% of the trials would end with an estimated MTD within the targeted toxicity range, but none in the overdosing range.

In Scenario 3 (high-toxicity scenario), only 38.8 % of the trials declared a dose as MTD with true DLT rate in the targeted toxicity range. In 17.1% of the trials, the estimated MTD was in the overdosing range. Scenario 4 (low-toxicity scenario) shows the best results, as would be expected.

Scenarios 5 and 6 showed worse operating characteristics; however, they are reasonable given the quite large deviations from the underlying BLRM.

The mean patient numbers range from 13.6 patients (Scenario 3) to 18.7 patients (Scenario 6), and the maximum number of patients was 21. Therefore, the patient numbers are as expected and increase when moving away from the high-toxicity scenario.

By reviewing the metrics presented in Table 10.3: 3, it can be seen that the model is generally conservative due to the overdose control criteria. In all scenarios except for the non-logistic case (scenario 5), the probabilities of recommending a dose with true  $P(DLT) \geq 25$  as MTD

are much smaller than the probabilities of recommending a dose with true  $P(DLT) < 25\%$  as MTD.

On-study recommendations based on the model are consistent with the clinical decision making process, and should be considered in conjunction with other available clinical information by the BI clinical trial team and study investigators in deciding the dose levels to be tested in order to determine the MTD estimate.

R version 3.3.2 was used for data scenarios and simulations.

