### 3. DESCRIPTION OF DESIGN AND TRIAL POPULATION

#### 3.1 OVERALL TRIAL DESIGN AND PLAN

This trial will consist of an SRD part followed by an MRD part. Both parts of the trial will be conducted non-randomized, open-label, and uncontrolled.

SRD part:

The starting dose is 0.06 mg. Dose-escalation will be restricted to a maximum of 200% from the previous dose up to doses of 0.5 mg, and to a maximum of 100% from the previous dose from dose 0.5 mg onwards. The maximum planned dose is 2 mg. For any dose-escalation cohort, at least 3 patients will be required. However, in the case that only 2 patients are evaluable and neither has experienced a DLE within the evaluation period (7 days after drug administration), then dose-escalation might occur based on these 2 patients if a joint decision of the Safety Monitoring Committee (SMC), see [Section 8.7](#) is reached. Refer to [Figure 3.1: 1](#) for a schematic representation of the dose escalation. For each dose group a single patient will be dosed on day 1 in each cohort, and only after a favorable safety and tolerability assessment on day 4 the remaining 2 patients will be dosed. A Bayesian logistic regression model (BLRM), based on a weakly informative prior distribution, and employing the escalation with overdose control (EWOC) principle (see [Section 7](#)) will be used for guiding the dose escalation [[R13-4803](#)]. Cohorts of patients will receive escalating doses of BI 836880. Each cohort will consist of newly enrolled patients.

The BLM provides estimates for the probability of observing an ocular DLE for each dose level in the study as patient information becomes available. The corresponding methodology is described in [Section 7.1](#) and in [Appendix 10.3](#). At any time in the trial, it will not be permitted to escalate to a dose which does not fulfil the EWOC principle.

The maximum tolerated dose (MTD) is considered as reached if at least 6 patients have been evaluated at a dose level which is the model's recommendation for the next dose cohort. Note the MTD will likely be the highest feasible dose, 2 mg, rather than the highest tolerable dose in a strict sense.

[figure not shown]

Figure 3.1: 1 Schematic representation of the dose escalation process in the SRD part of the trial

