The SMC recommends the size for the next dose escalation cohort. After all patients in a cohort have either experienced an ocular DLE or have been observed for at least the 7 days evaluation period without experiencing a DLE, the Bayesian model will be updated with the newly accumulated data. The overdose risk will then be calculated for each dose, and escalation will be permitted to all planned doses which fulfil the EWOC criterion and the respective escalation rule. As a sensitivity analysis, the BLRM might also be run again shortly before the SMC meeting, using all data available up to this time point. Based on the model results and on additional information (PK, pharmacodynamics [PD], patient profiles), the members of the SMC will reach a joint decision on the next dose level to be investigated.

If DLEs are observed in the first two consecutive patients of a previously untested dose level, subsequent enrolment to that cohort will be stopped. The BLRM will be re-run to confirm that the dose level still fulfils the EWOC principle. Based on this information, the SMC will evaluate whether the next patients will be enrolled at the same dose level, or if they will be enrolled at a lower dose level.

The SMC may decide on stopping the dose escalation after the above criterion for MTD is fulfilled. Further patients may be included to confirm that the EWOC criterion is still fulfilled.

MRD part:

The MRD part will consist of a first part (1 mg) with 11 treatment-resistant patients (cohort 1), a second part (2 mg) with 4 treatment-naïve patients (cohort 2), and approximately 12 frequently treated patients (cohort 3; inclusion criteria defined in [Section 3.3.2](#)). These are the two highest doses established by the SMC as safe and tolerable during the SRD part. Patients that had received a dose in the SRD part of the trial will not be included. In the MRD

Proprietary confidential information © 2022 Boehringer Ingelheim International GmbH or one or more of its affiliated companies

groups, patients will receive three consecutive doses over a 3-month period (once a month dosing, [Figure 3.1: 2](#)). The SMC will decide on dose escalation after 3 patients from the first MRD cohort have completed visit 5 (first follow up visit). In all patients included in the MRD parts of the trial, safety and efficacy will be studied to 12 weeks after the treatment period.

[figure not shown]

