### 3.3 SELECTION OF TRIAL POPULATION

This trial will recruit up to 18 patients in the SRD part (the SRD part was completed with 15 patients) and up to 27 patients in the MRD part (cohort 1, 2 and 3). Please refer to [Section 7.7](#) for details and justification.

Screening of patients for this trial is competitive, i.e. screening for the trial will stop at all sites at the same time once a sufficient number of patients has been screened. Investigators will be notified about screening completion and will then not be allowed to screen additional patients for this trial.

A log of all subjects enrolled into the trial (i.e. who have signed informed consent) will be maintained in the Investigator Site File (ISF) at the investigational site irrespective of whether they have been treated with investigational drug or not.

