#### SRD part:

The dose escalation will be guided by a Bayesian 2-parameter logistic regression model with overdose control [[R13-4803](#), [R13-4806](#)]. For a given dose, the EWOC criterion is that there should be less than 25% risk that the true ocular DLE rate is above 0.25.

The model is given as follows:

$$\text{logit}(\pi_d) = \log(\alpha) + \beta * \log(d/d^*),$$

where  $\text{logit}(\pi) = \log(\pi/(1-\pi))$ ,  $\pi_d$  represents the probability of having a DLE in the evaluation period at dose  $d$ ,  $d^* = 2$  mg is the reference dose, allowing for the interpretation of  $\alpha$  as the odds of a DLE at dose  $d^*$ , and  $\theta = (\log(\alpha), \log(\beta))$  with  $\alpha, \beta > 0$  is the parameter vector of the model.

The estimated probability of a DLE at each dose level from the model will be summarized using the following intervals:

- Target toxicity: [0.00, 0.25]
- Over toxicity: [0.25, 1.00]

The BLRM-recommended dose for the next cohort is the dose level with the highest posterior probability of the DLE rate falling in the target interval [0.00, 0.25) among the doses fulfilling EWOC. Thus, it should be unlikely (< 25% posterior probability) that the DLE rate at that dose will exceed 0.25. However, the maximum allowable dose increment for the subsequent cohort will be no more than 200% from the previous dose up to doses of 0.5 mg, and to a maximum of 100% from the previous dose from dose 0.5 mg onwards. Dose escalation will continue up to the 2 mg dose as long as the EWOC criterion for the next dose level is fulfilled. At the final dose, at least 6 treated patients are required. However, the SMC may decide to include additional number of patients at this dose level.

Since a Bayesian approach is applied, a prior distribution  $f(\theta)$  for the unknown parameter vector  $\theta$  needs to be specified. This prior distribution will be specified as a mixture of three multivariate normal distributions, i.e.

$$f(\theta) = a_1 f_1(\theta) + a_2 f_2(\theta) + a_3 f_3(\theta)$$

with  $a_i$ ,  $i = 1, 2, 3$  the prior mixture weights ( $a_1 + a_2 + a_3 = 1$ ), and  $f_i(\theta) = \text{MVN}(\mu_i, \Sigma_i)$ , the multivariate normal distribution of the  $i$ -th component with mean vector  $\mu_i$  and covariance matrix  $\Sigma_i$ , where

$$\Sigma_i = \begin{pmatrix} \sigma_{i,11}^2 & \sigma_{i,11}\sigma_{i,22}\rho_i \\ \sigma_{i,11}\sigma_{i,22}\rho_i & \sigma_{i,22}^2 \end{pmatrix}.$$

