#### **10.4      IMPLICATIONS OF CORONAVIRUS DISEASE 2019**

At the time of evaluating the fourth dose group of the SRD part in this trial, the COVID-19 pandemic emerged with worldwide impact on daily life. To allow for thorough evaluation of potential additional risks to trial participants in the course of this pandemic, the trial was temporarily put on hold in March 2020. At that timepoint, a total of ten patients had been treated with one single intravitreal injection of BI 836880. Available data did not show dose-limiting events, drug-related adverse events, nor systemic adverse events.

The trial has been re-initiated in July 2020 after potential additional risks for study participants with regard to COVID-19 have been evaluated.

Currently, there is no evidence that based on the pharmacological mechanism and existing non-clinical data the compound may increase the risk of progression of COVID-19 infection. No effects related to this MoA on the immune system are currently known. In conclusion, no change on the Benefit-Risk assessment of the compound in the context of the COVID-19 pandemic is foreseen.

The current study population is potentially at higher risk of COVID-19 infection due to background or concomitant diseases. As such, risk mitigation measures, such as measures to reduce patients' exposure will be implemented, if required. Enrolment will only happen when the local situation allows for patients to travel to the trial site, and all precautionary measures (e.g. use of protective personal/patients equipment) will be implemented, in line with local instructions and recommendations.

The investigators will take the totality of information related to each single patient and the local COVID-19 situation into consideration when performing the individual benefit-risk assessment on a case-by-case basis. Considering all aspects, the investigator will decide upon each patient's (continued) participation in the trial. BI as the sponsor, where required, will support the investigators in their decision finding. It is acknowledged that the investigator may decide to implement protocol deviations where this protects the safety, wellbeing and/or is in the best interest of the patient.

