6. GENERAL ANALYSIS DEFINITIONS

6.1 TREATMENTS

For basic study information on treatments to be administered, assignment of dose groups, selection of doses, refer to CTP Sections 3 and 4.

The trial will consist of an SRD part followed by an MRD part. Both parts will be conducted open-label, non-randomized, and uncontrolled.

It was planned to assign up to 42 patients in total, up to 15 in the SRD part (5 sequential dose groups comprising 3 patients each) and 27 in the MRD part (11 patients in dose group 1 (first cohort) and 16 patients in dose group 2 (4 patients from cohort 2 and 12 patients from cohort 3)).

For details of dosage and formulation see Tables 6.1:1 and 6.1:2 below.

Table 6.1: 1 Treatments and labels used in the analysis – SRD part

| Dose group | Treatment | | Short Label |
|------------|-----------|--|-------------|
| 1 | A | BI 836880, 80 mg/mL solution, 0.06 mg, ivt | BI 0.06mg |
| 2 | B | BI 836880, 80 mg/mL solution, 0.18 mg, ivt | BI 0.18mg |
| 3 | C | BI 836880, 80 mg/mL solution, 0.5 mg, ivt | BI 0.5mg |
| 4 | D | BI 836880, 80 mg/mL solution, 1.0 mg, ivt | BI 1mg |
| 5 | E | BI 836880, 80 mg/mL solution, 2.0 mg, ivt | BI 2mg |

Table 6.1: 2 Treatments and labels used in the analysis – MRD part

| Dose group | Treatment | | Short Label* |
|------------|-----------|---|-----------------------|
| 1 | F | BI 836880 Concentrate for Solution for Injection 80 mg/mL, diluted with Diluent to 20 mg/mL solution, 1.0 mg, ivt | BI 1mg q4w – cohort 1 |
| 2 | G | BI 836880 Concentrate for Solution for Injection 80 mg/mL, diluted with Diluent to 40 mg/mL solution, 2.0 mg, ivt | BI 1mg q4w – cohort 2 |
| 3 | H | BI 836880 solution for injection 40 mg/mL, 2.0 mg, ivt | BI 1mg q4w – cohort 3 |

* cohort 1: resistant patients, cohort 2: naïve patients, cohort 3; frequently treated patients

Cohorts 2 and 3 are displayed separately although belonging to the same dose group.

Section 7.3.4 of the CTP:

For BI 836880, the residual effect period (REP) after IVT administration is not known. Therefore, all AEs with an onset between start of treatment and the respective EOT visit will be assigned to the on-treatment period for evaluation.

Thus, no follow-up period is considered in this trial. The following separate study phases will be defined for the analyses of AEs:

- **Screening** (ranging from 0:00h (midnight) on the day of informed consent until the first administration time of BI 836880)
- **On treatment**

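### One row of the simulated operating characteristics (Table 10.3: 3, scenario 5) totals 91.0%, and the rule of at least 6 patients at the final dose is not reconciled with an SRD part that closed at 15

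*Protocol*

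**What the plan says.** **Simulation.** Appendix 10.3 simulates 1,000 trials for each of six dose-toxicity scenarios in cohorts of 3. It states that "A minimum number of 15 patients in the trial was required, and the maximum allowed patient number was 21". Table 10.3: 3 then gives three percentages per scenario: MTD with a true rate in the target range, MTD with a true rate in the overdosing range, and trials stopped early. The text on scenario 1 explains the third column: trials "stopped either because there was no MTD determined after 21 patients had been observed (3.5%) or because of high toxicity (2.1"%).

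**The 6-patient rule.** Section 3.1 treats the MTD as reached "if at least 6 patients have been evaluated at a dose level" that the model also recommends for the next cohort. Section 7.1 (SRD part) adds: "At the final dose, at least 6 treated patients are required". Section 3.1 also says: "The SMC may decide on stopping the dose escalation after the above criterion for MTD is fulfilled".

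**What was done.** Section 3.3: "This trial will recruit up to 18 patients in the SRD part (the SRD part was completed with 15 patients". SAP Section 6.1 describes the SRD part as "5 sequential dose groups comprising 3 patients each". Protocol Section 10.4 reports that, when the trial was paused while the fourth dose group was being evaluated, "a total of ten patients had been treated with one single intravitreal injection".

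**The concern.** Table 10.3: 3 is the plan's evidence on how well the design finds a dose. In an escalation trial with no power calculation, it stands where stated power would stand. A row that does not add up cannot be relied on. This one carries the largest overdose figure in the table (36.8%; the next largest is 17.1%, scenario 3), and it is the case the protocol itself names as the exception to its statement that the model is conservative.

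The second matter is what the SRD part can be said to have established. The current protocol defines the MTD and the final dose by a count of at least 6. The same protocol and the SAP describe a part that cannot have reached that count at 2 mg. A report written from these texts could apply either one.

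**Working it through.** **Step 1. Row totals of Table 10.3: 3.** Total = target + overdosing + early stopped.

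| Scenario | Sum | Total |
|---|---|---|
| 1 | 94.4 + 0 + 5.6 | 100.0 |
| 2 | 70.2 + 0 + 29.8 | 100.0 |
| 3 | 38.8 + 17.1 + 44.1 | 100.0 |
| 4 | 98.3 + 0 + 1.7 | 100.0 |
| 5 | 37.8 + 36.8 + 16.4 | **91.0** |
| 6 | 77.8 + 7 + 15.2 | 100.0 |

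The columns are exhaustive. In scenario 1 the third column is 3.5 (no MTD by 21 patients) + 2.1 (high toxicity) = 5.6, so it holds every trial without an MTD. Rounding is not an explanation: with 1,000 trials, 0.1% is one trial. The gap is 100.0 − 91.0 = 9.0 points, or 90 trials.

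**Step 2. Which cell?** If exactly one cell is wrong, it should be one of:
- target: 100 − 36.8 − 16.4 = 46.8%
- overdosing: 100 − 37.8 − 16.4 = 45.8%
- early stopped: 100 − 37.8 − 36.8 = 25.4%

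Re-simulating the stated rules (maximum 21, MTD declared only when the recommended dose is the one just tested) comes within about 3.5 points of the printed percentages in the other five rows. For scenario 5 it gives 40.0 / 29.9 / 30.1. If the MTD may be declared at any recommended dose with at least 6 patients, it gives 54.8 / 31.8 / 13.4. Neither matches the printed row, and the sponsor's stopping code is not visible, so re-simulation does not identify the cell. Global Amendment 1 changed the scenario 5 input at 0.18 mg from 0.100 to 0.010. The input used for the printed row is therefore worth confirming.

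**Step 3. How many patients can have received 2 mg?**
- As planned (SAP Section 6.1): 15 − 4 × 3 = 3.
- Independently (Section 10.4): ten patients were treated while the fourth group, 1.0 mg, was being evaluated. Groups are dosed in sequence and 15 were treated in all (Section 1.2), so at most 15 − 10 = 5 remain for 2 mg.
- Required: at least 6. With 3 at each lower dose, that needs 12 + 6 = 18 patients, as in hypothetical scenario 10 of Table 10.3: 1.

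**Step 4. Does the overdose criterion (EWOC) hold at 2 mg?** The model is logit(π_d) = log α + β·log(d/2), with the three-component prior of Table 7.1: 1. P(OD) is the posterior probability that π at 2 mg is at least 0.25, found by numerical integration. Check against the protocol's own figures at 2 mg:

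| Data | Recomputed | Stated |
|---|---|---|
| Prior | 0.306 | 0.304 |
| Table 10.3: 1, scenario 10 | 0.009 | 0.010 |
| Table 10.3: 1, scenario 11 | 0.222 | 0.220 |
| Table 10.3: 1, scenario 13 | 0.333 | 0.327 |

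Section 1.2 reports that no SRD event met the dose limiting event criteria. With 3 patients per dose and no such event, P(OD) at 2 mg is 0.026. Over every allocation of 15 with at least 2 per dose and 2 to 5 at 2 mg that fits Section 10.4, it runs from 0.013 to 0.035. The limit is 0.25.

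**The case against.** **The row is an erratum with little consequence.** Largely true. The protocol already singles out scenario 5 as the case where overdose selection is not much smaller than target selection. That remains so under each single-cell correction (46.8 against 36.8, 37.8 against 45.8, 37.8 against 36.8). No dose or endpoint analysis uses the row. It still cannot be right as printed, and under one correction overdose selection would exceed target selection.

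**The closure at 15 is disclosed and explained.** Section 3.3 states it, and the Amendment 5 rationale says that 1 mg and 2 mg were established with 15 patients. Section 7.7 allows fewer than 18. But Section 7.7 ties that to the criteria of Section 7.1, which include the 6; the stated SMC option to stop escalation applies once the criterion is met; and the amendment rationale waives nothing. The 6-patient sentences stand in the current text.

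**The reconciliation may exist out of sight.** This stands as a limit. Parts of the protocol and SAP are not visible, and the SMC minutes are not among the documents. The claim is only that no visible passage reconciles the two. SAP Section 4 lists changes to the planned analysis, and this is not among them.

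**Readings that go too far.** A reader might infer that 2 mg was carried forward without support. The documents do not say that: Section 7.1 rests the MRD doses on EWOC and Section 3.1 on the SMC, and EWOC holds by a wide margin. A reader might infer that the plan must declare that there is no MTD. That would settle a stopping rule that is for the sponsor to reconcile, and no visible passage declares an MTD. A reader might also see an error in Section 7.7 giving 18 where the simulation allows 21. Section 7.7 cites Appendix 10.3, which states 21, and about 18 agrees with the scenario 1 mean of 17.97.

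**Conclusion.** Two statements are wrong or inconsistent as written; both are minor.

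1. The scenario 5 row of Table 10.3: 3 is short by 9.0 points (90 of 1,000 trials). This is plain arithmetic and rests only on the columns being exhaustive, which the protocol's own account of scenario 1 supports. The wrong cell cannot be identified from the documents. The closeness of 16.4 to the row's mean patient number of 16.42 might suggest a copying slip, but that is conjecture.

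2. The requirement of at least 6 patients at the MTD or final dose was not met at 2 mg: 3 were planned and at most 5 are possible. This rests on the planned allocation in SAP Section 6.1 and, independently, on the count of ten in Section 10.4, given sequential groups and 15 patients in total.

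Neither point raises a safety concern. P(OD) at 2 mg is about 0.026 for five groups of 3, and at most 0.035 over the allocations considered, assuming no dose limiting event in the 15 patients.

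**What to change.** - Correct the scenario 5 row from the stored simulation output, and confirm that the run used the current input of 0.010 at 0.18 mg.
- Reconcile Protocol Sections 3.1, 3.3, 7.1 and 7.7 with SAP Section 6.1 on the 6-patient criterion. Which rule should govern is for the sponsor to decide.
- State in the SAP or the trial report which SRD conclusion the 15 patients support, for example the dose levels that fulfil EWOC with their P(OD).

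The cost is one table row from existing output, aligned wording in a few sections and a short statement. It needs no additional patients and no change to a dose decision or endpoint analysis. A new run is needed only if the stored one turns out to have used the superseded input.
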